Respiratory dysfunction is the leading cause of death in individuals with spinal cord injuries (SCIs). Nearly one-quarter of all SCI cases involve injury to the upper spinal cord segments which impairs neural activation of the diaphragm muscle and compromises breathing. Although mechanical ventilation can be life-saving after cervical SCI (C-SCI), it also triggers rapid and profound diaphragm muscle atrophy, thereby complicating (or even preventing) ventilator weaning. Intramuscular diaphragm stimulation, or diaphragm pacing, was developed to replace long-term ventilator support and is now used acutely post C-SCI (<4 months following injury) to promote ventilator weaning. Our group is part of a national team that initially reported 80% of C-SCI patients who underwent diaphragm pacing were successfully weaned from mechanical ventilation. Moreover, following electrode placement, gains in respiratory function were reported; remarkably, 36% of patients who received diaphragm pacing recovered independent breathing, enabling removal of the pacing electrodes. More recently, our team assessed the effects of diaphragm stimulation (pacing) longitudinally, from days to weeks after onset of diaphragm pacing demonstrating improvements in respiratory outcomes and EMG diaphragm activation (details below). However, there are clear gaps in how such data can be interpreted to determine the unique effects of diaphragm pacing since many factors affected outcomes in our longitudinal assessments (i.e. patient comorbidities, secondary complications after SCI, variances in ICU care, etc). Thus, these newly proposed experiments will examine the effects of diaphragm stimulation **within carefully controlled test sessions and examine effects immediately after a controlled period of stimulation**. This will allow us to determine the unique effects of diaphragm stimulation. Specifically, we will measure respiratory function and diaphragm activation prior to and following two ~1-hour time blocks and a single ~12-hour time block of diaphragm stimulation in patients with traumatic SCI. Our team is experienced in working with these patients and the conduct of these measurements. Overall, the proposed experiments will allow us to assess the effects of diaphragm stimulation on respiratory neural drive and breathing function in individuals with acute, traumatic C-SCI.

4. Introduction & Specific Aim:

Page 2 of 19

Protocol #: 201902285

IRB version: 10/09/2019

PI version: 2/3/2022

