More recently, our team assessed the effects of diaphragm stimulation (pacing) longitudinally, from days to weeks after onset of diaphragm pacing and showed improvements in respiratory outcomes including increased tidal volume, forced vital capacity, and maximum inspiratory pressures. Preliminary analyses also highlight increased EMG diaphragm activation evident after use of pacing. Thus, accumulating evidence suggests that diaphragm pacing exceeds the current standard of care (i.e. mechanical ventilation), and may represent a rehabilitation strategy to improve and even restore lost respiratory function. However, there are clear gaps in how such data can be interpreted to determine the unique effects of diaphragm pacing since many factors affected outcomes in our longitudinal assessments (i.e. patient comorbidities, secondary complications after SCI, variances in ICU care, etc). Thus, a primary goal in this protocol is to examine the effects of diaphragm stimulation within carefully controlled test sessions. Here, we propose to systematically evaluate the impact of diaphragm pacing on diaphragm neuromuscular activation (EMGs) and breathing capacity after two ~1-hour time blocks and a single ~12-hour time block of diaphragm stimulation in adults with acute, traumatic C-SCIs. This work represents an essential step in determining the efficacy of intramuscular diaphragm stimulation and its effects on respiratory function and neural control of the diaphragm following C-SCI.

Research AIM:

The aim of this protocol is to test the hypothesis that diaphragm pacing enhances neuromuscular activation of the diaphragm in adults with C-SCIs and improves respiratory function. We will test the hypothesis by recording activity of the diaphragm muscle (electromyograms; EMGs) from intramuscular pacing electrodes. Recording from these surgically implanted electrodes allows comparisons of electromyogram recordings before and after short periods of diaphragm pacing to better isolate the unique contribution of diaphragm pacing on neuromuscular diaphragm activation. This approach, in association with respiratory assessments, will enable us to better determine the unique impact of diaphragm pacing in patients with acute, traumatic C-SCIs.

5. Background & Preliminary Data:

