discharge planning or medical needs. Figure 1 highlights the improvement in respiratory outcomes (tidal volume, forced vital capacity, and max inspiratory pressures) over the course of these time points. Also highlighted are pilot results from 3 individuals showing increased diaphragm activation indicated by greater EMG activity from Early 1 to Early 2 time points (Figure 2).

Figure 1

[figure not shown]
[figure not shown]

Figure 2

Summary: Overall, these data combined with previous evidence suggests the possibility that diaphragm pacing is a potentially legitimate rehabilitation strategy to improve and even restore respiratory function.^{6-8,23} **The goal of this current protocol is to further examine the unique effects of diaphragm pacing in carefully controlled sessions shortly after implantation of the pacer.** This is an essential and critical next step in determining the efficacy of intramuscular diaphragm stimulation and its effects on respiratory neural drive and function after SCI.

6. Research Plan:

Inclusion and exclusion criteria.

Ten adults will be recruited who are ≥ 18 years old with acute, traumatic cervical spinal cord injuries (C-SCIs), classified according to the American Spinal Injury Association (ASIA) Impairment Scale (AIS) as A-C (complete SCI (A); motor complete SCI (B); motor incomplete with minimal motor function (C)),⁵⁸ affecting C1-C6 spinal cord segments, and who have been scheduled to undergo implantation of a diaphragm pacer, or who have recently received (in past 5-days) implantation of intramuscular diaphragm pacing electrodes due to severe respiratory impairments and dependence on mechanical ventilation. The inclusion criteria are based on our prior work with SCI patients and the injury characteristics of SCI patients with intramuscular pacing electrodes per clinical indications.^{6,7}

Exclusion criteria include: progressive neuromuscular diseases such as multiple sclerosis and myasthenia gravis, history of neurologic injuries such as stroke or prior SCI, chest wall injuries or deformities likely to influence breathing, pregnancy or cognitive impairments limiting study participation.

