Subject recruitment. Patients with acute, traumatic C-SCIs, scheduled to receive intramuscular diaphragm pacing OR who have recently received a diaphragm pacer (within past 5-days) will be recruited from UF Health Shands Jacksonville, a Level-1 trauma hospital serving North Florida. Potential study participants will be identified and informed of our study by [name] (study Co-I and expert in surgical diaphragm pacer implantation). UF Health Shands provides care to more than 500 acute, traumatic SCI patients annually, including 100 C-SCI patients. From this population, more than 50 patients are estimated to have C-SCIs categorized as AISA-C and are potential candidates for intramuscular diaphragm pacing. We aim to complete successful tests in 5 individuals. To complete these tests, we anticipate enrollment of 10 individuals who meet study inclusion criteria. Study procedures will be conducted at UF Health Jacksonville. [name] routinely provides medical and surgical care to this study population.

Of note, we will aim to recruit and enroll participants once they are scheduled to undergo diaphragm pacing (i.e. before pacer placement) so that the baseline tests can be performed prior to implantation and post-implant assessments can be performed shortly after implantation of the diaphragm pacer. We recognize that this process may not always be feasible due to complexities in the patient's medical condition or status. In some cases a patient may undergo implantation of the diaphragm pacer and the device may not be turned on for days. We, therefore, may enroll participants up to 5-days following pacer implantation. This strategy will help ensure that we meet enrollment goals and include those who would like to participate but had delayed use of the pacer.

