[name] will inform potential participants about the study and study-related procedures. Because [name] provides medical care and/or performs surgical diaphragm pacer implantation to this C-SCI population, he will identify potential participants who meet the inclusion/exclusion criteria. The specified criteria (determination of SCI injury level and status, respiratory function, medical history) are routinely part of this patient population's medical care and medical history. If a potential participant would like to learn more about the study, detailed information will be provided to the patient and their caregivers/family. The informed consent document will be used to guide this process. [name] also will notify the PI, [name] or a study Co-I that a patient would like to learn about the study and may be potentially interested in enrolling. Study coordinators, [name] or [name], who work closely with the study physicians, also may notify [name] and study Co-I. Based on this, [name] and/or a study Co-I will discuss the study with the patient and caregivers/family.

Study design & overview.

A single-factor quasi-experimental time-series study design is proposed. We will systematically evaluate diaphragm activation from EMGs recorded from intramuscular pacing electrodes and test inspiratory muscle strength and respiratory function in a small group of patients with acute, C-SCIs who have undergone implantation of diaphragm pacing electrodes.

An overview of the assessments is below, with details outlined in the subsequent sections.

Assessment Overview: We will study a small cohort of patients with acute C-SCIs following implantation of intramuscular diaphragm pacing wires. All individuals will meet inclusion criteria and will complete the informed consent process. Experiments are designed to determine if diaphragm stimulation (pacing) can produce neuroplastic changes in respiratory neural drive to the diaphragm and increase respiratory function. Neural drive to the diaphragm will be assessed by recording electromyograms (EMGs) from the intramuscular pacing wires following each of 3 blocks of diaphragm stimulation (Figure 3). Concurrent with these recordings from the diaphragm, respiratory function will be assessed using standardized clinical respiratory measures.

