After obtaining informed consent for participation in the study, [name] or designated members of the study team ([name], [name], DPT) will review the participant's medical records to obtain study-related medical and demographic data. Information obtained from the medical record will include information pertaining to health and medical history, details pertaining to the SCI, reports of medications and test results that could influence the individual's participation in the research procedures.. Additionally, clinical tests of sensory and motor function will be conducted to classify the level and severity of the individual's SCI. The tests of sensory and motor function are part of the American Spinal Injury Association (ASIA) Impairment Scale and the International Standards for Neurological Classification of Spinal Cord Injury. These clinical assessments are part of standard clinical care and include tests of sensation (dermatomes) and muscle strength via manual muscle testing (myotomes). These routine, standardized tests are done to clinically determine which segmental levels of the spinal cord demonstrate normal or impaired function. These tests also aid in determining if the SCI is clinically complete or incomplete. Determination of complete vs. incomplete is based on the sensory and motor function in the lowest sacral segments which control sensation and motor function at the anal sphincter. These standardized clinical tests are part of routine examination following spinal cord injury.

Baseline respiratory testing will be initiated once per day, up to 3 times on the days prior to diaphragm pacer implantation (Figure 3). Baseline respiratory tests include measurements of standard spirometry (tidal breathing, forced vital capacity or FVC) and maximum inspiratory pressures. We recognize that enrolling patients prior to diaphragm pacer placement may not always be feasible and we, therefore, may enroll participants up to 5-days following pacer implantation and will not obtain baseline (pre-implant) respiratory measures in these individuals.

*Pre-stimulation Assessment (post-diaphragm pacer placement)**

Page 7 of 19

Protocol #: 201902285

IRB version: 10/09/2019

PI version: 2/3/2022

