Following diaphragm pacer placement, the pre-stimulation assessment (prior to turning **on** the diaphragm stimulation) will be initiated approximately 18-24 hours after pacer implantation, once the patient is medically stable and able to participate. Waiting 18-24 hours after pacer implantation is standard of practice based on the procedures used by the diaphragm pacing surgical team ([name]). For individuals enrolled within 5-days after pacer implantation, the pre-stimulation assessment will occur as soon as possible after enrollment. The pre-stimulation assessment will include clinical respiratory tests and recording of diaphragm EMGs which are detailed in sections below. Pre-stimulation assessment will take approximately 2 hours to complete. To obtain a clear pre-stimulation assessment, two sets of tests will be conducted, about 1 hour apart. Ample time for rest breaks will be provided. The participant will be closely monitored and testing will be adjusted for each participant's comfort and medical needs.

*Post-tests (following periods of diaphragm stimulation)**

[figure not shown]
Post-testing will occur after 3 different blocks of diaphragm stimulation, and will occur with the stimulator turned off (Figure 3). These blocks are contiguous, meaning block 2 will begin immediately after post-testing in block 1, and block 3 will begin immediately after post-testing in block 2. See Figure below. Of note, turning the stimulator off and on is a typical occurrence in the medical setting. This allows patients to get used to the stimulation and also is necessary to change batteries in the control box. This externalized control box is easily accessible and has simple controls for turning the unit on and off. Post-tests will include the same battery of clinical respiratory assessments and diaphragm EMGs as pre-testing and will take approximately 1 hour to complete. The duration of stimulation varies for each block:

Block 1: ~1 hour of stimulation (no longer than 2 hours*) followed by post-test 1

Block 2: ~ 1 hour of stimulation (no longer than 2 hours*) followed by post-test 2

Block 3: ~ 12 hours of stimulation (no longer than 24 hours*) followed by post-test 3

Figure 3

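### The plan says it will establish what pacing alone does, but stimulation accumulates together with testing and elapsed time, and the only unstimulated EMG repeat has no stated use

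*Combined protocol and SAP*

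**What the plan says.** **Aim.** The abstract is the strongest statement: "This will allow us to determine the unique effects of diaphragm stimulation". Other places are softer. The Research AIM in section 4 speaks of recording before and after short pacing periods "to better isolate the unique contribution of diaphragm pacing on neuromuscular diaphragm activation", and the section 5 Summary wants to "further examine the unique effects of diaphragm pacing in carefully controlled sessions shortly after implantation of the pacer". Sections 4, 5 and 8 also present the work as a step in determining efficacy.

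**Design.** Section 6, Study design & overview: "A single-factor quasi-experimental time-series study design is proposed". Every participant has the same three blocks, and they are contiguous: "block 2 will begin immediately after post-testing in block 1, and block 3 will begin immediately after post-testing in block 2". No sham, no unstimulated period of matched length and no varied block order is described.

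**Unstimulated measurements.** Before stimulation, with EMG: "To obtain a clear pre-stimulation assessment, two sets of tests will be conducted, about 1 hour apart". Before implantation, with spirometry and inspiratory pressures only: "Baseline respiratory testing will be initiated once per day, up to 3 times on the days prior to diaphragm pacer implantation". Participants enrolled after implantation do not have the latter.

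**Analysis and reading.** The Statistical analysis paragraph names one Mann-Whitney comparison, before against after stimulator activation, for EMG and respiratory outcomes. The interpretation paragraph would take a gain as suggesting rehabilitation, and a change in activation as evidence for myogenic pathways.

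**The concern.** Short sessions within a person do reduce the problems the abstract names (comorbidities, secondary complications, differences in ICU care). They do not deal with what changes inside the session. The participant repeats maximal efforts, tires or learns, and recovers from surgery performed as little as 18-24 hours before. All of these advance in the same direction as cumulative stimulation.

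A rise after stimulation could therefore be credited to pacing when it reflects practice or recovery, or a real rise could be masked by fatigue. For EMG outcomes, and for respiratory outcomes in participants without a pre-implant baseline, the change between the two pre-stimulation sets is the only record of how far a person moves from one set to the next without pacing. The plan gives that change no stated role, although it intends to look for responders and non-responders and to use the results to justify a larger trial.

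**Working it through.** **1. Check of the schedule against the plan's own count.** Up to 3 baseline tests + 1 pre-stimulation assessment + 3 post-tests = 7; plus the ASIA examination = 8; 8 x $50 = $400. This matches the compensation paragraph if the two pre-stimulation sets count as one assessment. The plan states no power, alpha or effect size, so there is no sample-size figure to reproduce.

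**2. Inputs** (section 6, Pre-stimulation Assessment and Post-tests). Two pre-stimulation sets about 1 h apart, about 2 h in all; post-tests about 1 h each; blocks of about 1, 1 and 12 h, with maxima of 2, 2 and 24 h. Assumptions: each set lasts 1 h, and there is a gap g between the end of pre-set 2 and block 1. The text gives no gap, and Figure 3, which may show one, is not available in this copy.

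**3. Schedule with g = 0.**

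| | Pre 1 | Pre 2 | Post 1 | Post 2 | Post 3 |
|---|---|---|---|---|---|
| Earlier sets | 0 | 1 | 2 | 3 | 4 |
| Stimulation, h | 0 | 0 | 1 | 2 | 14 |
| Elapsed, h | 0 | 1 | 3 | 5 | 18 |
| Stimulation at maxima, h | 0 | 0 | 2 | 4 | 28 |
| Elapsed at maxima, h | 0 | 1 | 4 | 7 | 32 |

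Only the step from pre 1 to pre 2 advances testing and time while stimulation stays at zero.

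**4. Correlation with set number.** Mean stimulation is 17/5 = 3.4 h. Sum of products = 30; sums of squares 10 (set number) and 201 - 5 x 3.4² = 143.2 (stimulation). r = 30/√(10 x 143.2) = 0.79. The rank correlation is 0.975. Both are the same at the maximum durations and for any gap.

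**5. Correlation with elapsed hours.** With g = 0: mean elapsed 5.4 h; sum of products 265 - 5 x 3.4 x 5.4 = 173.2; sum of squares 359 - 5 x 5.4² = 213.2; r = 173.2/√(143.2 x 213.2) = 0.991. Over assumed gaps:

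| Gap before block 1 | Nominal | Maximum durations |
|---|---|---|
| 0 h | 0.991 | 0.997 |
| 1 h | 0.983 | 0.995 |
| 6 h | 0.925 | 0.971 |
| 12 h | 0.854 | 0.932 |
| 24 h | 0.758 | 0.856 |

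**6. What drift alone could look like (assumed values).** If each repeat added 5% of the starting value and stimulation added nothing, the changes from pre-set 2 would be +5%, +10% and +15% at post-tests 1, 2 and 3, which resembles a dose response. At 2% per repeat they would be +2%, +4%, +6%; at 10%, +10%, +20%, +30%.

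**7. What the unstimulated change can tell.** Let the SD of one set's result within a person be 1, with independent errors. A change between two sets has SD √2 = 1.414. The 95% half-width of its mean is t(0.975, n-1) x 1.414/√n:
- n = 10 (planned enrolment): 2.262 x 1.414/3.162 = 1.01
- n = 5 ("We aim to complete successful tests in 5 individuals"): 2.776 x 1.414/2.236 = 1.76

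It spans about 1 h. With g = 0, the intervals from pre-set 2 to post-tests 1, 2 and 3 are 2, 4 and 17 h (3, 6 and 31 h at the maxima). Any gap lengthens all three.

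**The case against.** The plan is candid about its level: it calls itself quasi-experimental and proof of concept, hedges its interpretation, and offers the results as grounds for a larger trial. It provides rest breaks, minimum intervals between manoeuvres, standardised procedures and a randomised testing order. These may reduce fatigue and order effects within the battery, but nothing applies the randomised order to the stimulation blocks, so the overlap remains.

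Four stronger readings are tempting, and the documents do not support them.
- *The unstimulated repeat is discarded.* The Statistical analysis paragraph is silent on how the two sets are used; it excludes nothing.
- *Nothing shows how the measures move without pacing.* That is true of EMG apart from the two pre-stimulation sets. Respiratory outcomes also have up to three pre-implant tests in participants enrolled before implantation.
- *No model with time and occasion terms could separate the effects.* Exact dependence (elapsed hours = stimulation hours + earlier sets) needs a zero gap and every set lasting exactly 1 h. A 1 h gap removes it, and the plan expects timing to vary.
- *Surgical recovery is wholly inseparable from stimulation.* Some participants start about 18-24 hours after implantation, and others may enrol up to 5 days after it, so time since surgery differs between people. This is a comparison between very few people, so it helps little.

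It is also fair to say that the proposed listing is imprecise and short. That limits what it can show, but it costs almost nothing.

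**Conclusion.** The point holds as a cheap improvement. A single-group, fixed-order series can describe change after stimulation; it cannot by itself establish the unique effect of stimulation. The overlap is substantial under every schedule examined: 0.79 with set number (rank 0.975), and 0.76 to 0.99 with elapsed hours (0.86 to 0.997 at the maximum durations). The elapsed-time figures rest on the assumed gap of 24 to 0 h and on 1 h per set.

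A reader might infer that the results will be biased upwards. The documents give no drift and no within-person variance, so neither the size nor the direction can be stated. What can be stated is that the plan's causal wording goes further than the design, and that the one unstimulated EMG step already being collected has no declared use. Whether the named test suits paired data is a separate question.

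**What to change.** **1. Statistical analysis paragraph.** Name pre-stimulation set 2, the last before stimulation, as the reference. For each participant and outcome, show the change from set 1 to set 2 beside the changes from set 2 to post-tests 1, 2 and 3, with recorded clock times and stimulation hours, and with omitted sets shown as missing. For respiratory outcomes, also show the pre-implant repeats where they exist. Keep this descriptive, with no subtraction and no test. Subtracting would give post-test 1 - 2 x set 2 + set 1, with variance 1 + 4 + 1 = 6 against 2 for the simple change, and would assume equal drift over unequal intervals.

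**2. Wording.** In the abstract, state the purpose as *describe change after diaphragm stimulation*. Soften the references to unique effects and to efficacy in sections 4, 5 and 8 in the same way. Qualify the rehabilitation and myogenic-pathway sentences in the interpretation paragraph with: *a gain cannot by itself be attributed to pacing rather than to repeated testing or recovery*.

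**Cost.** Text only, plus recording of clock times. No visit, test or participant is added, and the stimulation schedule is untouched. The limits should be stated with the listing: the unstimulated change is imprecise, tests omitted for medical reasons will thin it, and it is a rough reference for the early post-tests only, not for the 12 h block.
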